5.2 Adjustments for Covariates

For the continuous efficacy endpoints (e.g., change and percent change from baseline), disease duration and baseline value will be included as covariates in the statistical models, where disease duration, in years, will be calculated as follows:

$$\text{Disease duration (years)} = (\text{Randomization date} - \text{Initial onset date} + 1) / 365.25$$

Should the day be missing for the initial onset date, it will be imputed to the 1st of the month. Should both the day and month be missing for the initial onset date, they will be imputed to January 1st. Completely missing initial onset date will not be imputed.

For binary efficacy endpoints, Cochran-Mantel-Haenszel (CMH) tests will be stratified by the stratification factor for SALT I based on the value used by the IWRS at the time of randomization. If there are more than 10% of subjects who were mis-stratified, a sensitivity analysis will be conducted using the value from the clinical database.

5.3 Handling of Dropouts or Missing Data

See Section 5.2 for handling of completely or partially missing dates for disease duration.

See Appendix 2 for handling of completely or partially missing dates for prior and concomitant medications and AEs.

In DB Treatment Period, missing continuous efficacy data will not be imputed before being summarized using descriptive statistics and analyzed using a Mixed Model Repeated Measures (MMRM) as primary analysis (See section 10.1). For binary efficacy endpoints, subjects with missing data for any reason will be imputed as per the Non-Responder Imputation (NRI) method i.e., considered as a ‘non-responder’. As sensitivity analyses to the primary analysis of the primary efficacy endpoint and main analysis of the secondary efficacy endpoints, missing SALT I scores will be imputed as specified in sections 10.1 and 10.2.

In the OLE Period, missing efficacy data will not be imputed.

Unless otherwise specified, there will be no imputation for missing safety data for both study periods (DB Treatment Period and OLE Period).

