2. OBJECTIVES

Primary Objective

- To assess the safety and efficacy of etrasimod monotherapy (2 mg and 3 mg) in subjects with moderate-to-severe AA during the Double-Blind Treatment Period

Secondary Objectives

- To assess the long-term safety and efficacy of etrasimod monotherapy (2 mg and 3 mg) in subjects with moderate-to-severe AA
- To determine the plasma concentration of etrasimod 2 mg and 3 mg in subjects with moderate-to-severe AA

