6.8. Concomitant Therapy

6.8.1. Allowed Concomitant Therapy

There are no permitted medications for the treatment of AA for this study. Concomitant medications for medical conditions other than AA are permitted as clinically indicated, subject to specific protocol requirements outlined in Section 4.1 and Section 4.2. Any permitted medications also need to be approved in the country where it will be administered.

All medications (over the counter and prescribed) that are taken by subjects and all procedures that are performed during the Screening Period through the safety reporting period must be recorded in the eCRF along with:

- Reason for use
- Dates of administration, including start and end dates
- Dosage information, including dose and frequency

The Medical Monitor should be contacted if there are any questions regarding concomitant therapy.

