6.8.2. Prohibited Concomitant Therapy and Procedures

The following therapies are prohibited during the study:

- Topical, intralesional, or systemic corticosteroids
- Topical calcineurin inhibitors
- Topical or oral minoxidil
- Topical immunotherapy (eg, diphenylcyclopropenone, squaric acid)
- S1P receptor modulators (eg, fingolimod, siponimod, ozanimod, ponesimod), $\alpha 4\beta 1$ integrin receptor antagonists (eg, natalizumab)
- Phototherapy on scalp

- Any biological agents (eg, dupilumab, adalimumab, ustekinumab, secukinumab) regardless of indication
- Any investigational agent other than the study drug, including non-biologic agents and topical agents
- Moderate/strong inducers or inhibitors that inhibit or inducer at least two of the following: Cytochrome P450 (CYP) 2C8, CYP2C9, and CYP3A4 (eg, fluconazole, enzalutamide; [Table 4](#) for additional information refer to US FDA Drug development and drug interactions: Table of substrates, inhibitors and inducers ([Flockhart 2019](#)))

Table 4: Examples of Cytochrome P450 Inhibitors and Inducers

Cytochrome P450	Inhibitors (Strong/Moderate)	Inducers (Strong/Moderate)
CYP2C8	Clopidogrel, gemfibrozil, deferasirox, teriflunomide	Rifampin
CYP2C9	Fluconazole, amiodarone, felbamate, miconazole, piperine	Aprepitant, carbamazepine, enzalutamide, rifampin, ritonavir
CYP3A4	Boceprevir, cobicistat, danoprevir and ritonavir, elvitegravir and ritonavir, grapefruit juice, indinavir and ritonavir, itraconazole, ketoconazole, lopinavir and ritonavir, paritaprevir and ritonavir and (ombitasvir and/or dasabuvir), posaconazole, ritonavir, saquinavir and ritonavir, telaprevir, tipranavir and ritonavir, telithromycin, troleandomycin, voriconazole, aprepitant, ciprofloxacin, conivaptan, crizotinib, cyclosporine, diltiazem, dronedarone, erythromycin, fluconazole, fluvoxamine, imatinib, tofisopam, verapamil, clarithromycin, idelalisib, nefazodone, nelfinavir	Rifampin, apalutamide, carbamazepine, enzalutamide, mitotane, phenytoin, St. John's wort, bosentan, efavirenz, etravirine, phenobarbital, primidone

CYP, cytochrome P450

- Moderate/strong inhibitors or inducers of uridine diphosphate (UDP) glucuronosyltransferase (UGT) family 1 member A7 (UGT1A7)

In addition to being prohibited during the study, initiation of any of the following therapies will result in mandatory discontinuation from study drug:

- Topical JAK inhibitors

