- Systemic glucocorticoids (excludes inhaled or intranasal delivery that are considered topical for any reason)
- Immunoglobulin or blood products
- Systemic immunosuppressive/immunomodulating drugs (eg, cyclosporine, azathioprine, methotrexate), including oral JAK inhibitors
- All live or live-attenuated vaccines
- Any cell-depleting agents, including but not limited to rituximab

- Hair transplant, microblading, or micropigmentation of the scalp

For concomitant procedures:

- Subjects should not undergo major elective surgery while on study drug
- Subjects may not donate blood during the study and for 30 days after the last dose of study drug
- Subjects may not donate sperm, or oocytes during the study and for 30 days after the last dose of study drug

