8. REMOVAL OF SUBJECTS FROM THERAPY OR ASSESSMENT

8.1. Discontinuation of Study Drug

Study drug *must* be discontinued in the following instances:

- Unacceptable AE or AE that, in the judgment of the Investigator, is considered to not be in the best interest of the subject to continue study drug
- Subject request to discontinue for any reason
- Pregnancy during the study (Section [10.5.9](#))
- Termination of the study by the Sponsor or at the request of a regulatory agency or an Institutional Review Board (IRB) or Independent Ethics Committee (IEC)
- Lost to follow-up
- Criteria met from cardiac HR monitoring to discontinue study drug (Section [10.5.7.4](#))
- Confirmed lymphocyte measurement $< 0.2 \times 10^9$ cells/L (Section [10.5.7.2](#))
- Received a prohibited concomitant medication that required discontinuation of study drug (Section [6.8.2](#))

- Other

Study drug *may* be discontinued in the following instances:

- Subject noncompliance
- Protocol deviation
- Drug-induced liver injury (Section 10.5.7.1)

Subjects who discontinue treatment prematurely, regardless of the reason, should be instructed to return for an ET visit within 1 week of when the last dose of study drug was taken, and for Safety Follow-Up Visits 2 weeks and 4 weeks after the last dose of study drug (ie, SFU 1 and SFU 2) (Appendix 1 and Appendix 2). If a subject fails to attend the follow-up visits, all reasonable efforts will be made to contact the subject to ensure that he/she is in satisfactory health. All contacts and contact attempts must be documented in the subject's medical record.

Whenever possible, subjects should continue on study and complete the remaining study visits and assessments even when study drug has been discontinued.

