7.2 Protocol Deviations

PDs with a start date before the date of first dose in OLE will be considered a DB PD while PDs with a start date on or after the date of first dose in OLE will be considered an OLE PD.

A blinded data review will be conducted before the primary database lock by the Medical Monitor and Sponsor to classify each PD occurring during the DB Treatment Period as 1) important or non-important and 2) major or minor (refer to the PD Management Plan [PDMP]). Another data review will be conducted before the final database lock by the Medical Monitor and Sponsor to classify each PD occurring during the OLE period as 1) important or non-important and 2) major or minor (refer to the PDMP).

During the review conducted before the primary database lock for DB Treatment Period, major PDs potentially having an impact on the SALT I-related primary and secondary efficacy endpoints will be identified by the Medical Monitor and Sponsor and will lead to the exclusion from the PPS. These PDs might include, but are not limited to:

- Violation of eligibility criteria
- Receiving incorrect study treatment
- Compliance with study treatment < 80%
- Chronic use of prohibited medication while on study treatment

The number of events and the frequency count and percentage of subjects with at least one important PD, with a least one major PD, with at least one major PD potentially having an impact on the SALT I-related primary and secondary efficacy endpoints, and with at least one PD associated with COVID-19 will be summarized for the DB Treatment Period by treatment group, deviation category, and deviation sub-category using the randomized set. Important PDs, major PDs, and PDs related to COVID-19 will be summarized similarly overall using the randomized set and for the OLE period using the OLE SAF.

A listing of all protocol deviations will be provided. Important PDs, major PDs, major PDs potentially having an impact on the on the SALT I-related primary and secondary efficacy endpoints, and COVID-19 related PDs will be flagged in this listing.

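### A Week 24 SALT I score recorded after a prohibited hair-regrowth therapy can count as response for the randomised arm, because non-response is assigned only to missing data

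*SAP*

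**What the plan says.** - **Objective.** Protocol 2: "To assess the safety and efficacy of etrasimod monotherapy (2 mg and 3 mg) in subjects with moderate-to-severe AA during the Double-Blind Treatment Period".
- **Other hair-loss treatment.** Protocol 6.8.1: "There are no permitted medications for the treatment of AA for this study". Protocol 6.8.2 has two lists. One holds therapies that are prohibited but carry no rule of their own for stopping study drug, such as "Topical or oral minoxidil", topical or intralesional corticosteroids and topical immunotherapy. The other holds therapies whose start also ends study drug: topical JAK inhibitors, systemic glucocorticoids, and systemic immunosuppressants "including oral JAK inhibitors".
- **Follow-up after stopping.** Protocol 8.1: "Whenever possible, subjects should continue on study and complete the remaining study visits and assessments even when study drug has been discontinued". Protocol 9.5 says the same in substance.
- **Data used.** Protocol 11.4 puts all available data into the models. SAP 4.3 takes scheduled visits as scheduled and invokes the Table 1 windows for early-termination, unscheduled and retest values. For subjects never treated in the open-label extension, Table 1 closes the Week 24 window six days after the last treatment day.
- **Missing data.** SAP 5.3: "For binary efficacy endpoints, subjects with missing data for any reason will be imputed as per the Non-Responder Imputation (NRI) method". The MMRM for the continuous endpoints uses observed data. SAP 10.2 refers back to 5.3 for the responder endpoints.
- **Per Protocol Set.** SAP 7.2 gives "Chronic use of prohibited medication while on study treatment" as one possible reason for exclusion, in a list that is expressly open-ended and is settled at blinded review before the primary lock. SAP 10.1 and 10.2 use this set only for sensitivity analyses.

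**The concern.** A subject who starts another therapy that regrows hair, and who then attends Week 24, has an observed SALT I score. Nothing in SAP 5.3, 10.1 or 10.2 treats that score differently from one obtained on randomised drug alone. In the responder analyses, the subject can be a success for the arm to which they were randomised. In the MMRM, the regrowth enters that arm's Week 24 mean.

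This sits badly with a monotherapy objective. The arms are small, so one or two such subjects can move a response rate or a mean noticeably. If the rule is settled only after unblinding, the choice will be open to challenge.

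**Working it through.** **1. Can such a score reach the main analysis?** There are two cases.

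*Therapy that ends study drug (e.g. a JAK inhibitor).* Study drug stops, but visits continue where possible (Protocol 8.1, 9.5). If the subject attends the scheduled Week 24 visit, the outcome depends on how SAP 4.3 is read:
- By the text of 4.3, scheduled visits are used as scheduled. The score is observed and enters both the responder analysis and the MMRM.
- If the Table 1 limit (last treatment day + 6) also bound scheduled visits, a score taken later than that would have no Week 24 slot. The subject would become a non-responder under NRI and add no Week 24 value to the MMRM. The SAP does not say this.

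*Therapy without its own stopping rule (e.g. minoxidil, a topical or intralesional corticosteroid).* The subject may still be on study drug at Week 24. The score is then inside the window on either reading and is used.

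**2. Does a sensitivity analysis target this event?** No. SAP 10.1 lists seven for the continuous endpoint and SAP 10.2 lists five for the binary endpoints. The MI analyses fill only missing scores. The Per Protocol Set analyses may exclude such a subject, but the named example requires chronic use while on study treatment.

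**3. The plan's own figure.** SAP 3.2 gives a difference of 20, SD 17.8, two-sided 0.05, and completers of 20 (3 mg), 5 (2 mg) and 10 (placebo). The noncentrality is 20 / (17.8 × √(1/n₁ + 1/n₂)).
- 20 v 10: 20 / 6.894 = 2.90, 28 df, power 79.97% (stated 80%).
- 5 v 10: noncentrality 2.05, 13 df, power 47.6% (stated 47%).

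Both reproduce, so these inputs are a sound base for an illustration.

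**4. Shift in response rate per extra responder.** Under NRI the denominator is the Full Analysis Set, not completers. The planned placebo numbers are 12 in Cohort 2 and 12 in Cohort 1, and Cohort 1 subjects with baseline SALT I of 95 or more are left out of the set. So 24 is an upper bound.
- 1/12 = 8.3 points.
- 1/24 = 4.2 points.

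**5. Shift in mean difference.** Assume one placebo subject gains g extra points of improvement, everyone else is unchanged and the SD stays at 17.8. New difference = 20 − g/n. The range of g and the case of 20 placebo completers (Cohort 1 added) are assumptions.

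| Placebo completers | g | Shrinkage | Difference | Power, 3 mg (n = 20) |
|---|---|---|---|---|
| 10 | 0 | 0 | 20 | 80% |
| 10 | 30 | 3 | 17 | 66% |
| 10 | 80 | 8 | 12 | 39% |
| 20 | 0 | 0 | 20 | 93% |
| 20 | 30 | 1.5 | 18.5 | 89% |
| 20 | 80 | 4 | 16 | 79% |

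The same event in an active arm would inflate the difference instead.

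**The case against.** **The window may already remove the clearest cases.** If Table 1 binds scheduled visits, a subject who stops study drug well before Day 155 has no Week 24 value and is a non-responder, much as proposed here. This stands in part: a reader should not conclude that every score after a JAK inhibitor is certain to be used. But 4.3 does not apply the windows to scheduled visits, and the limit does nothing for subjects still on study drug.

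**Few such scores may exist.** Continued attendance is asked for only where possible. Early stoppers are also sent to an early-termination visit and to follow-up visits at two and four weeks, the second of which is the end-of-study visit (Protocol 9.4). Eligible placebo subjects receive open-label etrasimod from Week 24, which weakens the reason to look elsewhere. This stands: the frequency is unknown.

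**Blinded review can already exclude these subjects.** The SAP 7.2 list is not closed, and these therapies are prohibited throughout the study. It would therefore be too strong to say that the Per Protocol Set misses anyone who stops study drug and then starts another therapy. But exclusion is not required, and the set supports only sensitivity analyses.

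**Using all data is a legitimate treatment-policy choice.** The study is exploratory, without Type I error control, and the word monotherapy does not by itself fix an estimand strategy. This has force for the primary MMRM: setting later scores to missing rests on a missing-at-random assumption and changes the question. It has less force for the responder endpoints, where counting such subjects as non-responders is standard and needs no imputation model.

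**Conclusion.** The gap is real but bounded. The SAP assigns non-response only to missing data and has no rule for scores taken after a prohibited therapy, so such a score can count as response although the objective is monotherapy efficacy.

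The size is conditional. It is nil if nobody uses such a therapy, and the documents give no rate. One placebo responder of this kind moves the placebo rate by 8.3 points (12 subjects) or 4.2 points (24, an upper bound). Under the stated assumptions, one user shrinks the mean difference by 3 to 8 points with 10 placebo completers, or 1.5 to 4 with 20.

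Two stronger readings are not supported:
- **That the bias must hide an effect of etrasimod.** It is plausible that untreated subjects are likelier to seek another therapy, but the documents do not show it, and use in an active arm inflates the effect.
- **That one responder adds 10 or 5 points.** That divides by completers, whereas NRI keeps dropouts in the denominator.

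The change is a cheap improvement to the main binary analyses. For the continuous endpoints it belongs in a sensitivity analysis.

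**What to change.** 1. **SAP 5.3 and 10.2.** From the start of any Protocol 6.8.2 therapy that can affect scalp hair, count the subject as a non-responder for the binary SALT I endpoints. Flag these cases at the blinded review already planned before the primary lock. Keep the as-observed analysis as a sensitivity analysis.
2. **SAP 10.1.** Add a sensitivity MMRM/MI in which SALT I scores after such therapy are set to missing, and state the missing-at-random assumption. Leave the primary MMRM as it is.
3. **SAP 7.2.** Drop the restriction to use during study treatment from the Per Protocol Set example.
4. **SAP 4.3.** State whether the Table 1 windows bind scheduled visits after study drug has stopped. Report the number of users by arm.
5. **SAP 12.** Record the new non-response rule as a change, since Protocol 11.4 ties non-response to missing data.

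**Cost.** SAP wording and one flag built from concomitant-medication dates that Protocol 6.8.1 already collects. The main binary estimate is no longer treatment-policy, which the retained as-observed analysis covers. No clinical management rule changes.

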5.4 Interim Analysis and Data Monitoring

No formal interim analysis of efficacy is planned.

5.5 Multicenter Studies

Study will be conducted at multiple (approximately 29) study sites in the United States and Canada. All sites will be combined for the statistical analyses owing to the small number of subjects expected per site.

5.6 Multiple Comparisons/Multiplicity

No formal testing strategy or adjustments of the Type I error will be employed for the primary and secondary efficacy endpoints. Estimates and two-sided 95% Confidence Intervals (CIs) for treatment groups and from treatment comparisons will be reported in an exploratory manner.

5.7 Examination of Subgroups

Subgroup analysis by below variables will be performed using descriptive statistics only based on the following analysis set for the primary and secondary efficacy endpoints of the DB Treatment Period (refer to Sections 10.1 and 10.2, respectively) to explore whether the treatment effects are

consistent across different subgroups. Median will be derived based on subjects specific to each analysis set.

- Sex (male, female) – FAS
- Race (white, non-white) – FAS
- Age (\leq or $>$ median) – FAS
- Baseline SALT I score (\leq or $>$ median) – FAS
- Duration of AA from initial onset (\leq or $>$ median) – FAS
- Current disease duration (0 - $<$ 2.5 years, 2.5 years - $<$ 5 years, \geq 5 years): from onset of current episode – FAS
- Baseline AASIS (\leq or $>$ median) – FAS
- Baseline AA-QLI (\leq or $>$ median) – FAS

Additionally, subgroup analysis by below variables will also be performed using descriptive statistics only based on the following analysis set for demographic and other baseline characteristics (refer to Section 6.1), disposition of subjects (refer to Section 7.1), primary and secondary efficacy endpoints of the DB Treatment Period (refer to Sections 10.1 and 10.2, respectively), and exploratory efficacy endpoint of percent change from baseline in peripheral lymphocyte counts of the DB Treatment Period (refer to Section 10.3).

- Cohort (1 or 2) – FAS
- Baseline SALT I score ($<$ 50 or \geq 50) – FAS
- Baseline SALT I score ($<$ 50, \geq 50 to $<$ 95 or \geq 95) – Randomized Set
- Current disease duration ($<$ 5 years, \geq 5 years): from onset of current episode – FAS

The overall summary of AEs during the DB Treatment Period (refer to Section 11.1) and summary of vital signs of the observed and change from pre-dose values at Day 1 and Week 24 (refer to Section 11.3) will also be summarized by these subgroups for SAF.

6 SUBJECTS CHARACTERISTICS

6.1 Demographic and other Baseline Characteristics

Demographics and baseline characteristics will be summarized with descriptive statistics based on the Randomized Set, FAS, and Safety Set for the DB Treatment Period and on the Open-Label

Extension Safety Set, Open-label Extension FAS for the OLE Period. The list of demographics and baseline characteristics to be summarized includes:

- Age (years) – at time of informed consent
- Sex (male, female)
- Ethnicity (Hispanic or Latino, not Hispanic or Latino, not reported, unknown)
- Race (White, American Indian or Alaska Native, Asian, Native Hawaiian or other Pacific Islander, Black or African American, not reported)
- Baseline height (cm)
- Baseline weight (kg)
- Baseline BMI (kg/m^2)
- Baseline BMI (kg/m^2) by category ($\leq 25 \text{ kg}/\text{m}^2$, $> 25 \text{ kg}/\text{m}^2$)
- Cohort (Cohort 1, Cohort 2)
- AA disease duration (years) since initial onset (refer to Section 5.2)
- AA disease duration (years) for current episode, where AA disease duration for current episode, in years, will be calculated as follows: (Date of randomization – Start date of current episode) + 1
- AA disease duration (years) for current episode by category (0 - < 2.5 years, 2.5 - < 5 years, ≥ 5 years)
- Baseline SALT I score
- Baseline SALT I score by category (< 50 , ≥ 50), (< 50 , $50 - < 95$, ≥ 95), (< 95 , $95 - < 100$, ≥ 100)
- Baseline AASIS
- Baseline AA-QLI

A listing of all demographics and baseline characteristics will be provided.

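### SAP 6.1 labels current-episode duration as years, but its formula returns days; programmed literally, it puts every eligible subject in the ≥ 5 years category

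*SAP*

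**What the plan says.** The SAP uses two disease durations.

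- **Since initial onset (SAP 5.2).** This is the model covariate, introduced by "where disease duration, in years, will be calculated as follows". The formula is the randomization date minus the initial onset date, plus 1, all divided by 365.25.
- **Current episode (SAP 6.1).** This is introduced by "where AA disease duration for current episode, in years, will be calculated as follows". The expression that follows is "Date of randomization – Start date of current episode) + 1", with the opening bracket just before the first word and nothing after the final 1. Neither document gives another formula for this variable.

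The current-episode variable is used in these places:

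- SAP 6.1 summarizes it continuously and by category: "AA disease duration (years) for current episode by category (0 - < 2.5 years, 2.5 - < 5 years, ≥ 5 years". The summaries cover the Randomized Set, FAS, Safety Set, OLE Safety Set and OLE FAS.
- SAP 5.7 uses the same three levels, measured "from onset of current episode", as a subgroup for the primary and secondary endpoints.
- SAP 5.7 also uses a two-level split (< 5, ≥ 5 years) for demographics, disposition, the primary and secondary endpoints and lymphocyte counts and, in the Safety Set, for the overall adverse event summary and the Day 1 and Week 24 vital signs.
- SAP Appendix 3 lists five subgroup tables by current disease duration in the first batch of the primary analysis: 14.1.1.1.3.2.4, 14.1.2.2.2.4, 14.2.1.3.9, 14.2.2.3.9 and 14.2.5.1.2.4.

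**The concern.** The unit in the sentence and the unit that the expression produces do not agree. A date difference plus 1 is a count of days. The SAP itself uses that form for days elsewhere: Study Day in Section 4.2 and duration of exposure in Section 9. Only the current-episode formula combines that form with a label of years.

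At stake is whether the current-duration tables carry any information. The cut-points are 2.5 and 5 and the values run to hundreds or thousands, so a literal program would produce subgroup tables with a single populated level and a baseline summary in the wrong unit.

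**Working it through.** **Inputs**

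- Current-episode formula: SAP 6.1, date difference + 1.
- Parallel formula: SAP 5.2, (date difference + 1) / 365.25.
- Cut-points: 2.5 and 5 years (SAP 5.7 and 6.1).
- Eligible durations: at least 6 months and < 5 years in Cohort 2 (Protocol 4.1, SAP 3.1); at least 6 months and < 8 years in Cohort 1 (SAP 3.1).
- In whole days, taking 365.25 days per year: differences of about 183 to 1825 in Cohort 2 and about 183 to 2921 in Cohort 1.

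The plan states no figure that depends on this formula, so there is none to reproduce.

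**Step 1. The formula as written, beside the 5.2 form**

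| Date difference (days) | As written: difference + 1 | Level as written | (difference + 1) / 365.25 | Level after division |
|---|---|---|---|---|
| 183 | 184 | ≥ 5 | 0.504 | 0 to < 2.5 |
| 548 | 549 | ≥ 5 | 1.503 | 0 to < 2.5 |
| 914 | 915 | ≥ 5 | 2.505 | 2.5 to < 5 |
| 1825 | 1826 | ≥ 5 | 4.999 | 2.5 to < 5 |
| 1827 | 1828 | ≥ 5 | 5.005 | ≥ 5 |
| 2921 | 2922 | ≥ 5 | 8.000 | ≥ 5 |

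The ratio of the two results is 365.25 in every row. As written, a value below 5 needs a difference of 3 days or less, which eligibility rules out. Counting 6 months as 181 days still gives 182.

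**Step 2. All eligible whole-day values**

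These are counts of possible day values, not of expected subjects.

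| Range (days) | Formula | 0 to < 2.5 | 2.5 to < 5 | ≥ 5 |
|---|---|---|---|---|
| Cohort 2, 183–1825 (1643 values) | As written | 0 | 0 | 1643 |
| | Divided by 365.25 | 730 | 913 | 0 |
| Cohort 1, 183–2921 (2739 values) | As written | 0 | 0 | 2739 |
| | Divided by 365.25 | 730 | 913 | 1096 |

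After division the levels separate, and no eligible Cohort 2 value reaches 5 years.

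**Step 3. Can a generous reading save the text?**

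- *Treat the difference as already in years, then add 1.* A difference of 548 days becomes 548 / 365.25 + 1 = 2.50 and moves up a level. A difference of 1461 days becomes 1461 / 365.25 + 1 = 5.00 and moves to ≥ 5. Of the 1643 Cohort 2 values, 730 (44%) land in the wrong level.
- *Append the divisor to the end of the line.* Because the bracket closes before the + 1, this divides only the 1. A difference of 548 gives 548 + 1 / 365.25 = 548.003, still in days.

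The expression has to be re-bracketed as well as divided.

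**Step 4. Reach into the models**

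SAP 10.1 specifies disease duration in years, with reference to Section 5.2, as a covariate in the primary mixed model. The ANCOVA analyses in 10.1 and 10.3 also adjust for disease duration in years, which 5.2 defines for the continuous efficacy endpoints. That variable is duration since initial onset and already carries the divisor. The current-episode variable enters no model.

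**The case against.** The strongest reply is that the text contradicts itself rather than giving a clear wrong rule. The sentence says years, the bullet label says years, the cut-points are in years, and Section 5.2 shows the conversion. A programmer would probably divide. If not, values of 183 and above under a years heading, or an empty < 5 years level, would be hard to miss in the tables and in the baseline listing. This stands as a limit on the likely harm: the collapse is conditional on literal programming. It does not make the formula right, and a silent correction would be an undocumented departure from the SAP.

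Three stronger readings might be inferred, and the documents do not support them.

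- **That the primary analysis is at risk.** SAP 5.7 limits these subgroups to descriptive statistics, SAP 5.6 sets no formal testing strategy, and the model covariate is the correctly scaled variable.
- **That the < 5 / ≥ 5 split is the plan's check on the wider Cohort 1 entry limit (< 8 years against < 5 years).** The cut-point matches the Cohort 2 limit, but the SAP gives no such purpose. Nor would cohort differences go unexamined: SAP 5.7 has a separate cohort subgroup, and 10.1 has sensitivity analyses that adjust for cohort (#5), use Cohort 2 only (#6) and exclude the 3 mg arm with cohort adjustment (#7). Analysis #6 already contains only episodes under 5 years among eligible subjects. None of these splits Cohort 1 by duration, so something would be lost, but less than the whole comparison.
- **That the 5.2 rule for partial dates must be carried over as part of this correction.** Section 5.2 names only the initial onset date. How to treat a partial episode start date is a separate question of missing detail.

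**Conclusion.** The formula in SAP 6.1 is wrong as written: it omits the division by 365.25 and returns days under a label of years. Followed literally, it inflates continuous summaries 365.25-fold, classes 100% of eligible subjects as ≥ 5 years and leaves every lower level empty. The conclusion rests on the eligibility minimum of 6 months in both cohorts and on reading a date difference as days, as the SAP does elsewhere.

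The reach is limited to descriptive output: the baseline tables and the current-duration subgroup summaries. Primary and secondary model estimates, confidence intervals and p-values do not change. The correction should be made because the stated rule gives a wrong result and costs almost nothing to repair; it is not a threat to the trial's main conclusion.

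**What to change.** In SAP 6.1, replace the expression with:

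AA disease duration for current episode (years) = (Date of randomization – Start date of current episode + 1) / 365.25

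The + 1 belongs inside the bracket, as in Section 5.2. In Section 5.7, add a reference to this formula at both current-duration subgroups, so that the baseline tables and the subgroup tables use one definition.

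The cost is one line of wording and two cross-references. Design, data collection, sample size and models are untouched. If the sponsor also wishes to state how partial episode start dates are handled, that is a separate choice and not part of this correction.
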